We will assess social skills by administering the Social Skills Questionnaire (SSQ);⁵² and social functioning using the Adolescent Social Self-Efficacy Scale (ASSES).⁵³

Suicidality Assessment

The Columbia Suicide Severity Rating Scale (C-SSRS) will be used to screen for and assess suicidal ideation. Those that do not meet inclusion criteria for this assessment will not be enrolled in the study. Participants who do not meet this criteria but express interest in the study may be reengaged and reassessed following a 2-month period. The C-SSRS will be repeated at the *End of Study* (V3) Visit to screen for any changes in suicidal ideation over the course of the study. The C-SSRS may be re-administered during the intervention period, as needed, should there be any concerns for safety or increasing symptoms.

Intervention Embedded Assessments

Cognitive Biases. Participants in both the WASABI and active control arm will complete embedded assessments immediately before and after the 12-week intervention. Additionally, for participants assigned to WASABI, during the intervention and program use period, WASABI weekly collects performance data on two cognitive assessments that capture attention bias assessment, and an interpretation bias assessment. Participants assigned to

receive WASABI will also complete a weekly SPAI-B assessment. Performance on these assessments will be modeled longitudinally to examine if these measures can serve as potential moderators and mediators of treatment efficacy.

The primary outcome measures, including assessment adherence, dCBGT and IM engagement, EMA, SPAI-B and overall program completion rates, reported adverse effects, usability ratings and clinician burden, will be used to assess feasibility, acceptability and usability of WASABI.

Secondary outcomes include clinical ratings of anxiety and social anxiety symptoms (LSAS-CA), self-report inventories of social anxiety symptoms (SPAI), broad measures of anxiety (MASC-2), as well as measures that capture social skills (SSQ), and social functioning (ASSEs).

Description of Protocol Devices (Software Program)

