- *Standardized Self-Report Questionnaires.* WASABI includes standardized self-reports of social anxiety (SPAI-B), and weekly assessments that implicitly evaluate core cognitive operations known to be impaired in social anxiety (e.g., attention bias, interpretation bias). The SPAI-B consists of 16 items using a 5-point Likert scale (1–5). It assesses the cognitive, somatic, and behavioral symptoms (triple-response-system) and captures interactional and performance-provoking socially anxious situations. In the attention bias assessment, neutral and negative faces are presented for a limited time, followed by a letter that is displayed in the region of the screen where the neutral face was. Participants need to identify the letter as quickly as possible. In the interpretation bias assessment, a series of ambiguous images is presented for a limited time (for example, a situation in which one friend walks past another without acknowledgement), followed by a screen where three images with clear emotional valence are concurrently presented. Participants need to choose the image that captures the emotion that best explains the ambiguity of the previous images. The rationale behind the assessment is that participants with interpretation bias may develop expectations that ambiguous situations are more likely to end negatively.
- *WASABI Alerts.* If WASABI detects clinically-significant social anxiety through EMA metrics (EMA Thoughts, EMA Feelings, EMA Goals), cognitive biases assessments, and the Social Phobia and Anxiety Inventory-Brief (SPAI-B), the monitoring clinician will receive an alert that cues them to connect via Instant Messaging with the participant. The algorithm will be used to alert the WASABI clinician when a trial participant reaches clinically significant social anxiety, so that symptom exacerbation can be addressed over Instant Messaging.

EMAs, cognitive biases assessments and self-reports are meant to support standard clinical care by providing additional structured tools for an individual to use to address cognitive biases that often co-occur with anxiety. To complete these activities, a participant opens a

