Digitally delivered Cognitive Behavioral Group Therapy (dCBGT): The WASABI Clinician will lead weekly dCBGT structured sessions through videoconferencing. Sessions replicate the protocol described in "Cognitive-behavioral group therapy for social phobia in adolescents",⁵⁴ with 12 weekly sessions that center CBT content around the young person's developmental context, needs, and capacities, and adapt it to the unique developmental issues characteristic of adolescence (e.g. ascendancy of the peer group, identify formation, propensity towards limit testing). Sessions 1-4 focus on psychoeducation on recognizing and understanding social anxiety symptoms (e.g., avoidance cycle that maintains anxiety over time; rationale for exposure to overcome avoidance cycle). Sessions 5-6 implement cognitive restructuring (focusing on the identification/modification of dysfunctional thoughts) and social skills training. Session 7-8 include instruction in exposure principles and role-play/modeling of exposure exercises. Sessions 9-11 focus on in vivo exposure to anxiety provoking situations. In vivo exposure during these sessions focuses on anxiety provoking situations that can be created within the social setting of the video chat, such as a person giving a speech or singing a song, members engaging in "small talk" with each other, or people altering their appearance in a socially conspicuous way (e.g., messy hair, wearing silly attire). Session 12 focuses on how to avoid personal pitfalls and relapse. Adjustments may be made to the dCBGT treatment

described in “Cognitive-behavioral group therapy for social phobia in adolescents” during COVID-19 to allow for a more appropriate treatment given current shelter-in-place and distance-learning procedures that may not allow for replication of the traditional protocol. Participants are assigned “homework” focused on practicing specific skills in anxiogenic, in vivo situations to promote skills generalization and anxiety/fear extinction learning.

Participants in the active control will complete two sessions of embedded assessments, one immediately before and one after the 12-week intervention. The embedded assessments include two cognitive assessments—an attention bias assessment and interpretation bias assessment—and the SPAI-B assessment.

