We hypothesize that the innovative features of WASABI will improve the quality of treatment delivery and facilitate the generalization of trained skills into real-world settings. The measures collected to determine the efficacy of the program for this trial are clinical ratings of anxiety and social anxiety symptoms (LSAS-CA), self-report inventories of social anxiety symptoms (SPAI), broad measures of anxiety (MASC-2), self-report inventories of social skills (SSQ), and self-report inventories of social functioning (ASSES). To test this hypothesis, we will use a linear mixed model approach. We will first compare treatment and active control groups in the ITT population to determine if any differences in baseline demographic, characterization, outcomes variables, or total program use time remain after the randomization process. Any such factors that show trend level significant differences ($p < 0.1$) will be noted and used as covariates in the linear mixed model analysis. The criterion for statistical significance is $p < 0.05$. Results with $p < 0.1$ will be described as trends.

Performance on the attention bias and interpretation bias assessments will be modeled longitudinally to examine if these measures can serve as potential moderators and mediators. To test if the attenuation of attention and interpretation biases mediates improvements in outcome measures, we will use repeated-measures linear mixed modeling to test in the active group the effects of WASABI on LSAS-CA, SPAI, SSQ and ASSES, and then model outcomes as a function of performance improvements on the attention bias and interpretation bias assessments.

Because we are interested in examining the ecological validity of WASABI, we will not restrict the analyses only to participants who adhered to all intervention requirements. Within-group effect sizes (Cohen's d) will be computed using the mean change scores (post-intervention minus baseline) and the change score SDs.

These measures will be analyzed to power the pivotal study proposed for Phase II. For the FDA, we will collect data documenting that WASABI meets its design requirements when used in the field by clinicians and patients, and that clinicians deem its risk/benefit ratio as acceptable and view it as adequate/appropriate for the target population.

Data Management

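### As described, the attention bias task shows the letter at one location only, so attention bias cannot be separated from speed and practice in the mediator/moderator models

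*Protocol*

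**What the plan says.** **The task.** The protocol describes it under Experimental Treatment Intervention, in the bullet on standardized self-report questionnaires. A neutral and a negative face appear briefly, "followed by a letter that is displayed in the region of the screen where the neutral face was". The response is speeded: the task is to name that letter without delay. No other trial type is described. The interpretation bias task in the same bullet is different: the participant chooses among three images, and no letter appears.

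**Its purpose.** That bullet calls the tasks "weekly assessments that implicitly evaluate core cognitive operations known to be impaired in social anxiety". A few lines later, the text describes the same activities as "providing additional structured tools for an individual to use to address cognitive biases that often co-occur with anxiety".

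**Who does it, and when.** Under Intervention Embedded Assessments: "Participants in both the WASABI and active control arm will complete embedded assessments immediately before and after the 12-week intervention". For the WASABI arm during the intervention, "WASABI weekly collects performance data on two cognitive assessments that capture attention bias assessment, and an interpretation bias assessment". For control, under Active Control Program: "Participants in the active control will complete two sessions of embedded assessments, one immediately before and one after the 12-week intervention".

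**How it is used.** Under Data Analysis: "Performance on the attention bias and interpretation bias assessments will be modeled longitudinally to examine if these measures can serve as potential moderators and mediators". The mediation step is specified in the active group, with outcomes modelled on improvement in performance on the two tasks. The bias tasks are also one of several inputs to the WASABI alerts. The SAP (section 2, Feasibility) says that potential mediators and moderators are defined in advance, but it does not name or score them.

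**The concern.** Attention bias towards threat is a contrast: how much slower a person responds when the letter replaces the neutral face than when it replaces the negative one. With one location there is nothing to subtract. A participant who becomes quicker through repetition gives the same data as one whose bias has fallen.

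The mediator model is fitted in the arm that repeats the task weekly, while symptoms may be falling under dCBGT. Faster responses and lower symptom scores could then move together for unrelated reasons and be reported as mediation through reduced attention bias. The moderator question suffers too, because a baseline value from one location would mainly rank participants by general speed.

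A letter tied to the neutral face also rewards attending to that face. Repetition could then act as practice in doing so, which is hard to square with a purely measuring role.

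**Working it through.** The documents give no bias index, reliability or power for this task, so there is no stated figure to reproduce. The check is whether the described design can estimate the quantity that the analysis needs.

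**1. One session.** Let response time = s + b × p, where s is general speed, b is bias, and p = +1/2 for a letter at the neutral face and −1/2 at the negative face.
- Neutral location only: every row of the design matrix is (1, 1/2). The second column is half the first, so the rank is 1 of 2. The mean estimates s + b/2 and nothing else.
- Both locations: the rank is 2 of 2, and b = mean time at neutral − mean time at negative.

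**2. Pre and post.** Add a time indicator t (0, 1), giving the columns intercept, t (practice), p (bias) and p × t (change in bias).
- Neutral only: the last two columns are half the first two, so the rank is 2 of 4. The observed change is Δs + Δb/2. A fall of D fits Δs = −D with Δb = 0 (pure practice) as well as Δs = 0 with Δb = −2D (pure bias reduction).
- Both locations: the rank is 4 of 4, and change in bias separates from practice.

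More sessions or participants do not help, since every added row has the same dependence. Accuracy does not help either: at a single location it has no contrast.

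**3. How weak a proxy is the single-location time?** The documents give no standard deviations, so these are assumptions: between-person SD of speed 50 to 150 ms, SD of bias 10 to 40 ms, the two independent. The share of variance due to bias is (SD_b/2)² / [(SD_b/2)² + SD_s²].
- Most favourable: 20² / (20² + 50²) = 400/2,900 = 13.8%, correlation 0.37.
- Least favourable: 5² / (5² + 150²) = 25/22,525 = 0.1%, correlation 0.03.

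**4. Repetition by arm.**

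| Reading | WASABI | Control | Difference |
|---|---|---|---|
| 12 weekly plus before and after | 14 | 2 | 12 |
| Before and after counted among the weekly sessions | 12 | 2 | 10 |
| 70% of weekly sessions done: 0.7 × 12 + 2 | 10.4 | 2 | 8.4 |

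The 70% is an assumption. The SAP states that rate for EMA prompts and the weekly SPAI-B, not for the bias tasks.

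**The case against.** The strongest reply is that the task is described in one sentence, which never says that the letter is at the neutral face on every trial. Negative-location trials may exist undescribed, so a statement that all trials are at the neutral location would read silence as fact. That stands, and the point is therefore conditional on the task as written. It does not remove the need to act: either the task cannot yield a bias score, or the plan omits the trial types and score on which its own model depends.

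A reader might also infer four stronger things that the documents do not support.

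- *That the cognitive-bias question as a whole cannot be answered.* Interpretation bias is an image-choice task without a letter. It shares the unequal repetition and the active-group analysis, but not this defect.
- *That WASABI contains an undeclared active component.* The protocol lists the weekly cognitive assessments among the treatment tools of the experimental arm and describes them as helping to address biases. The treatment role is declared; it is not reconciled with the measuring role.
- *That the arm comparison of bias scores is confounded.* Neither document specifies such a test. The session imbalance would confound one if it were added, but the problem in the plan is practice within the active group.
- *That the clinical comparison is biased.* Weekly repetition is part of the package under test. It clouds the mechanism, not the comparison of dCBGT+WASABI with dCBGT.

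Finally, bias is an exploratory mediator or moderator, not a primary or secondary outcome, in a trial that says it lacks power for an augmentation effect. This limits the severity.

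**Conclusion.** The point holds for attention bias. With the letter at the neutral face only and no score defined, bias and change in bias cannot be estimated (rank 1 of 2 in one session, 2 of 4 for pre/post), and the attention-bias half of the mediator/moderator analysis is not identifiable. Practice gains in the arm with up to 14 sessions could be reported as attenuated bias.

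This goes beyond missing detail, because following the stated task and model as written leads to that misreading. It should be corrected, but it does not threaten the trial's main purpose: feasibility outcomes, clinical outcomes and interpretation bias are untouched by letter position.

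The conclusion assumes that the described trial type is the only one and that the active group means the WASABI arm. The rank result needs no numerical assumption beyond the additive model. The 0.1% to 13.8% range depends wholly on the assumed standard deviations, and 14 sessions is a ceiling.

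**What to change.** 1. Show the letter equally often, in random order, at the neutral and negative locations. Pre-specify in protocol and SAP the within-session difference (mean time at neutral minus mean time at negative) as the only attention-bias score in the mediator/moderator models. General speed cancels in it, and so does practice to the extent that it affects both locations alike.
2. If negative-location trials already exist, describe them and use that score.
3. If the task cannot be changed, drop attention bias as mediator and moderator, keep interpretation bias, and describe the attention task as part of the WASABI package.
4. Reconcile the two descriptions of the tasks, as implicit evaluation and as tools to address biases.
5. The alert description should be reconciled by the sponsor with what this score can measure. No alert rule is proposed here.

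**Cost.** A change to the task and a few sentences of text; the documents do not say how the task is configured, so the programming effort cannot be judged. Each location's times rest on half the trials. For n trials with equal variance σ², the difference has variance 2 × σ²/(n/2) = 4σ²/n, against σ²/n for the mean of all trials, so its standard error is twice as large. Data from a neutral-only version would not be comparable. The unequal number of sessions between arms remains, and any later between-arm comparison of bias should acknowledge it.
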